6.5. Derived and Transformed Data

6.5.1. Study Day

Study day is the day relative to the date of first dose. Day 1 is defined as the date of first dose.

If date of first dose is not present, then date of randomization is used to calculate the study day.

Assessments without timestamp collected on the same date as the first date of study drug administration are considered to occur before the first dose of study drug administration.

For visits (or events) after first dose, day is calculated as:

- Study day=visit (or event) date-date of first dose+1

For visits (or events) before first dose, day is calculated as:

- Study day=visit (or event) date-date of first dose

The quantity 'days since first dose' is defined as:

- Days since first dose=visit (or event) date–date of first dose+1

The quantity 'days since last dose' is defined as:

- Days since last dose=visit (or event) date-date of last dose

For summaries that present distribution of time expressed in weeks and months, weeks are defined as days divided by seven and months as days divided by 30.4.

6.5.2. Visit Windows

Analysis visits and their windows are defined using derived study day (Section 6.5.1) instead of relying on visit labels in the clinical database because clinical visits may occur outside protocol-specified windows. Study day and days after last dose are calculated using the actual date of each scheduled and unscheduled assessment and compared to the target for each analysis visit as specified in Table 4 and Table 5. They are included in analyses of safety and efficacy as follows:

- Efficacy analyses for endpoints assessed through Week 100 use the analysis windows in Table 4, irrespective of whether or not a patient is receiving treatment of study drug.
- Efficacy analyses for endpoints assessed during the follow-up period after Week 100 use the analysis window in Table 4 irrespective of how long a patient has been off-treatment.
- Protocol version 6 eliminated the off-treatment period from Week 48 to Week 52. Patients completing the Week 52 visit prior to consenting to protocol version 6 will be considered “off-treatment” at Week 52. All other patients are expected to be on-treatment at Week 52. Week 52 analysis values in Table 4 will not be used in the efficacy analyses unless otherwise specified. Week 52 values are only summarized descriptively because of the mix of on-treatment and off-treatment values.
- Safety analyses use the analysis windows defined in Table 4 so long as the patient is receiving treatment of study drug. Once a patient permanently discontinues study treatment, safety data are summarized according to time since last dose as defined in Table 5.

Unless otherwise specified if a parameter is assessed or measured more than once within a visit window, the one that is closest to the protocol-scheduled time point (i.e., target) is used for the purposes of data analysis and summary.

If 2 assessments are equidistant from a target, the earlier assessment is used. If 2 assessments are on the same day, the average of 2 assessments will be used for non-laboratory parameters. For laboratory parameters, if both an original and retest result are available in the laboratory dataset, the original result will be used and the second (i.e., “retested”) result will be ignored.

One exception is that 2 scheduled chemistry values (including eGFR) are collected within the Week 52 (prior to protocol version 6), Week 104, Week 108, and Week 112 analysis windows.

Protocol specified 2 off-treatment chemistry values collected within the Week 52 (prior to protocol version 6), Week 104, Week 108 and Week 112 analysis window at A and B visits. At Week 52, Week 104, Week 108, and Week 112 visits, the 2 off-treatment measurements that are in the analysis window and closest to the target day specified in Table 4 are averaged for the purpose of data summary and analysis. All values included in the Week 103, 104, 108, and 112 analysis windows must also be assessed after last dose.

Records from visits not closest to the target study day, and therefore not used in analyses, are presented in by-patient data listings.

Table 4. ANALYSIS VISIT WINDOWS

Analysis Visit	Label	Target		Analysis Window
		Study Day ^a	Days After Last Dose	
1	Week 1	7	-	$2 \leq \text{study day} \leq 10$
2	Week 2	14	-	$11 \leq \text{study day} \leq 21$
4	Week 4	28	-	$22 \leq \text{study day} \leq 35$
6	Week 6	42	-	$36 \leq \text{study day} \leq 49$
8	Week 8	56	-	$50 \leq \text{study day} \leq 70$
12	Week 12	84	-	$71 \leq \text{study day} \leq 126$
24	Week 24	168	-	$127 \leq \text{study day} \leq 210$
36	Week 36	252	-	$211 \leq \text{study day} \leq 294$
48	Week 48	336	-	$295 \leq \text{study day} \leq 350$
52	Week 52	364	-	$351 \leq \text{study day} \leq 406$
64	Week 64	448	-	$407 \leq \text{study day} \leq 490$
76	Week 76	532	-	$491 \leq \text{study day} \leq 574$
88	Week 88	616	-	$575 \leq \text{study day} \leq 658$
100	Week 100 ^b	700	-	$659 \leq \text{study day} \leq 720$
103	Week 103 ^c	721	21	$721 \leq \text{study day} \leq 727^{\text{d}}$ or $21 \leq \text{after last dose} \leq 27^{\text{e}}$
104	Week 104 ^c	728	28	$728 \leq \text{study day} \leq 755^{\text{d}}$ or $28 \leq \text{after last dose} < 55^{\text{e}}$
108	Week 108 ^c	756	56	$756 \leq \text{study day} \leq 783^{\text{d}}$ or $56 \leq \text{after last dose} \leq 83^{\text{e}}$
112	Week 112 ^c	784	84	$784 \leq \text{study day} \leq 806^{\text{d}}$ or $84 \leq \text{after last dose} < 106^{\text{e}}$

^a Study Day is relative to the date of first dose (Section 6.5.1).

^b Week 100 is the end of the dosing interval and should coincide with the last dose.

^c Including off-treatment values only.

^d Analysis windows are based on study day for patients who discontinued treatment early. Analysis windows are based on days after last dose for patients who complete treatment. Last dose for analysis is the Week 100 dose.

^e Analysis windows are based on days after last dose for patients who complete treatment. Last dose for analysis is the Week 100 dose.

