#### **5.1.2.1. Fluid Overload**

Similar to endothelin receptor antagonists (ERAs) in certain patient populations, including bosentan in advanced congestive heart failure and avosentan in advanced CKD, bardoxolone methyl treatment was found to be associated with an increased risk for fluid overload and heart failure hospitalizations in the BEACON trial, which enrolled patients with Stage 4 CKD (eGFR 15 to 29 mL/min/1.73 m^2) and type 2 diabetes. The overall increased risk for fluid overload and heart failure events with bardoxolone methyl appeared to be limited to the first three to four weeks after initiation of treatment. Elevated BNP and prior hospitalization for heart failure were identified as risk factors that contributed to increased risk for these events. The increased risk for these events from bardoxolone methyl treatment had not been observed in six previous CKD studies, which were conducted mostly in patients with Stage 3b CKD (eGFR of 30 to 44 mL/min/1.73 m^2), patients with hepatic dysfunction, cancer patients, or healthy volunteers.

Review of admission notes and narrative descriptions for heart failure hospitalizations in BEACON indicates that heart failure in bardoxolone methyl-treated patients was often preceded by rapid fluid weight gain (several kilograms within the first weeks of treatment initiation) and was not associated with acute renal decompensation or acutely reduced left ventricular contractility. Available data from BEACON and other studies suggest that bardoxolone methyl treatment can differentially affect hemodynamic status according to the clinical condition of patients and likely promotes fluid retention in patients with more advanced renal dysfunction and other recognized risk factors associated with heart failure at baseline.

In a Phase 2 dose-ranging study of the efficacy and safety of bardoxolone methyl in patients with pulmonary hypertension (LARIAT), risk mitigation procedures were employed to reduce the potential for bardoxolone methyl-induced fluid overload; these procedures excluded patients with the identified risk factors and ensured close monitoring for fluid retention within the first month of treatment. To date, the risk for acute fluid overload AEs with bardoxolone methyl in late-stage CKD patients has not been observed in PH patients.

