#### **5.1.2.2. Transaminase and Gamma-Glutamyl Transpeptidase (GGT) Elevations**

In clinical studies of bardoxolone methyl, almost all patients had increases of transaminase enzymes above baseline upon initiation of treatment, which followed a consistent pattern. These increases were not associated with elevations in bilirubin, and hepatotoxicity has not been observed. In BEACON, fewer hepatobiliary SAEs were observed in the bardoxolone methyl arm than in the placebo arm. The elevations begin immediately after initiation of treatment or an increase in dose; they peak approximately two to four weeks later. In most patients, transaminase elevations were mild, but approximately 4% to 11% of patients experienced an elevation greater than 3X the upper limit normal (ULN). The elevations resolved to levels less than the ULN in most patients with elevations, within two weeks after peak values while patients continued taking study drug. Patients who experienced elevations to greater than 3X the ULN sometimes required additional time to resolve. While some patients have had elevations to

above 3X the ULN, persistent elevations to above 3X the ULN have not been observed, and the elevations did not recur once resolved, unless caused by other factors.

Bardoxolone methyl regulates gamma-glutamyl transpeptidase GGT, a known Nrf2 target gene protein. In clinical studies, low level GGT elevations during treatment were common, mild, and typically lasted longer than alanine aminotransferase (ALT)/ aspartate aminotransferase (AST) elevations. Bilirubin levels in patients experiencing transaminase or GGT elevations due to treatment with bardoxolone methyl either remained at baseline levels or decreased. The ALT, AST, and GGT elevations were generally self-limiting in patients who continued treatment with study drug.

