7.1. Overall Study Design	
Approximately <del>550</del> 850 patients will be enrolled.
 
All patients in the study will follow the same visit and assessment schedule. Following randomization on Day 1, patients will be scheduled to be assessed during treatment at Weeks 1, 2, 4, 6, 8, 12, 24, 36, 48, 52, 64, 76, 88, and 100, and 104, and by telephone contact on Days 3, 10, 21, 31, 38, and 45. <del>Patients will not receive study drug during a 4 week withdrawal period between Weeks 48 and 52. They will re-start treatment at Week 52 at the same dose they were receiving at Week 48 and will continue study drug treatment through Week 100. Patients will also be scheduled to be assessed at an in-person follow-up visit at Weeks 103, 104, 108, and 112 after the end of treatment, respectively, four weeks after the end of treatment.</del>
 
<del>The primary efficacy endpoint-</del> Efficacy endpoints will be analyzed after all enrolled patients have completed the study and the database has been locked, their Week 52 visit (or have terminated from the trial). <del>The key secondary efficacy endpoint will be analyzed after all enrolled patients have completed their Week 104 visit (or have terminated from the trial).</del> All enrolled patients are expected to remain on
	
Update in primary endpoint that impacts the sample size since the W108 value will be used for endpoint analysis, regardless of how long a patient has been off treatment. A dilution in the difference between treatment groups at Week 108 is expected due to contribution of early treatment discontinuation patients

Section	Version 6	Rationale

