4.3. Sample Size Considerations

4.3.1. Primary Endpoints

With 850 patients enrolled, the study will have approximately 80% power to detect a difference between the 2 treatment groups in change from baseline eGFR of 2.3 mL/min/1.73 m². The power calculation was based on a 2-sample t-test as an estimate for the planned analysis of covariance (ANCOVA) analysis and assumes the following:

- Overall two-sided Type I error rate total of 0.05;
- Standard deviation of change from baseline in eGFR of 12 mL/min/1.73 m²;
- Analyses are based on the intent-to-treat (ITT) population;
- Missing data will be imputed using multiple imputation.

PASS 13 software was used to calculate sample size.

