6. GENERAL CONSIDERATIONS FOR DATA ANALYSES AND HANDLING

The efficacy and safety analyses use the analysis sets defined in Section 6.3. Patient listings (as appropriate) of all analysis data that support summary tables and/or figures are provided along with their source data. The summary tables do not include measurements from patients excluded from the pre-defined analysis sets or extra measurements (such as unscheduled or repeat assessments) not closest to the target study day unless specified otherwise, but the patient listings do include these data. Missing data are not imputed, unless otherwise specified. In general, patient listings are sorted by treatment group, patient number and assessment date (time and parameter, as applicable).

Any laboratory value (including eGFR), vital sign assessment, or ECG value collected after ESKD is considered invalid and will be treated as missing.

Efficacy and safety data collected while a patient has temporarily discontinued study drug will be included in analyses. All data will be presented in by-patient listings.

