9.1.2. Summaries of Adverse Events

Treatment-emergent adverse events and OTEAEs are summarized by treatment. For each treatment, SOC, and PT, the number and percentage of patients reporting an event is calculated. In summary tables, SOC is presented alphabetically and events within each SOC are presented by decreasing frequency count. Additionally, summary tables of events within PTs are presented by decreasing frequency count may be generated.

Summary tables (number and percentage of patients and events) of TEAEs (by SOC and PT) are provided by treatment as follows:

- All TEAEs
- All related TEAEs (definitely, probably, or possibly related)
- All TEAEs by severity
- All serious TEAEs (including deaths)
- All non-serious TEAEs
- All related serious TEAEs (including deaths)
- All TEAEs leading to permanent discontinuation of study drug
- All TEAEs leading to study drug interruption
- All TEAEs leading to dose de-escalation
- TEAEs by time to onset (≤ 12 weeks and > 12 weeks)
- TEAEs exhibited in $> 5\%$ of patients in either treatment group

Listings are provided showing:

- All AEs
- Deaths
- SAEs
- AEs leading to permanent discontinuation of study drug
- TEAEs leading to study drug interruption
- TEAEs leading to dose de-escalation

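### The SAP labels pre-version-6 patients off-treatment at Week 52, but its by-visit safety rules and its adverse-event onset table do not carry that through

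*SAP*

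**What the plan says.** The version 6 summary of changes in the protocol records the earlier schedule. Drug was withheld for four weeks from Week 48, and then: "They will re-start treatment at Week 52 at the same dose they were receiving at Week 48". That text is superseded and serves here only as a record of what those patients received.

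The SAP knows about the break in several places:

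- 6.5.2 labels anyone who completed Week 52 before consenting to version 6 as off-treatment, keeps Week 52 out of the efficacy analyses, and adds: "Week 52 values are only summarized descriptively because of the mix of on-treatment and off-treatment values".
- 7.1 counts patients on and off treatment between Weeks 48 and 52 separately.
- 9.2 removes the break from exposure and compliance, and summarises days since last dose for patients off treatment at Week 52.

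The by-visit safety rules are different:

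- 6.5.2: "Safety analyses use the analysis windows defined in Table 4 so long as the patient is receiving treatment of study drug". Table 5, based on time since last dose, takes over only after permanent discontinuation.
- Section 6: "Efficacy and safety data collected while a patient has temporarily discontinued study drug will be included in analyses".
- 6.5.2.1 treats every assessment up to 20 days after last dose as on-treatment. 9.5.2 uses the same limit for its worst-value tables.
- 9.5, 9.7 and 9.9 summarise laboratory values, vital signs and ECGs by visit and treatment group, with no split by drug status at Week 52.
- 9.1 lets the treatment-emergent period run from first dose to 30 days after last dose. 9.1.2 lists "TEAEs by time to onset" with one cut at 12 weeks, and does not say from which dose onset is counted.

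**The concern.** Safety and tolerability is one of the two primary objectives. A Week 52 mean that averages patients on drug with patients four weeks off drug describes neither group. In a line graph, a sustained but reversible effect would appear to fade at Week 52 and come back at Week 64. Week 52 is also one of only three treatment-period ECG visits in the current schedule (Weeks 48, 52 and 100).

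The restart raises a second issue. The protocol links several known effects to starting drug. Of transaminases it says "The elevations begin immediately after initiation of treatment or an increase in dose". Of fluid overload, in the phase 3 trial in stage 4 CKD with type 2 diabetes, it says that the excess risk "appeared to be limited to the first three to four weeks after initiation of treatment". If a restart can trigger such events, an onset table with no restart rule could present them as late events.

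**Working it through.** The plan gives no figure on this point, so there is none to reproduce. The check has three parts.

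**1. One pre-version-6 patient followed through the rules.** Table 4 of the SAP puts Week 48 at study day 336 and Week 52 at day 364, so the nominal gap is 364 − 336 = 28 days. The patient restarts and stays on drug.

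| SAP rule | Status of the Week 52 value |
|---|---|
| 6.5.2, label for pre-version-6 patients | off-treatment |
| 6.5.2, condition for using Table 4 | read literally, not met: no drug is being taken |
| 6.5.2, trigger for Table 5 | not met: no permanent discontinuation |
| Section 6, temporary stops | included |
| 6.5.2.1 and 9.5.2, last dose = final dose | on-treatment, because it precedes the last dose |

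If last dose instead meant the Week 48 dose, 28 days exceeds the 20-day limit, but Table 5 would still not apply. The value is then either in the Week 52 column or in no table. Section 6, and the remark in 6.5.2 that the Week 52 summaries contain a mix, both point to the Week 52 column.

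**2. Size of the blurring, as an illustration.** Protocol 5.1.1 gives eGFR changes in the phase 2 Alport study of 10.4 mL/min/1.73 m² at 48 weeks on drug and 4.1 four weeks after withdrawal. Let f be the share of bardoxolone patients in the Week 52 column who are off drug. The documents do not give f; the range below is assumed.

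- Mixed mean = (1 − f) × 10.4 + f × 4.1
- Shortfall against the on-drug mean = f × (10.4 − 4.1)/10.4 = f × 0.606

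| f | Mixed mean | Shortfall |
|---|---|---|
| 10% | 9.360 + 0.410 = 9.770 | 6.1% |
| 25% | 7.800 + 1.025 = 8.825 | 15.1% |
| 50% | 5.200 + 2.050 = 7.250 | 30.3% |
| 75% | 2.600 + 3.075 = 5.675 | 45.4% |

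**3. Where restart events fall.** Protocol 5.1.2.2 puts the transaminase peak two to four weeks after a start or dose increase. After a restart on day 364 that is day 378 to 392 (364 + 14 to 364 + 28), or weeks 54 to 56. Counted from first dose, this is far beyond 84 days, so the events go into the row for more than 12 weeks. Counted from the restart, they occur at 14 to 28 days and go into the other row. SAP 6.5.1 defines time since first dose and nothing from a restart; 9.1.2 names no origin.

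**The case against.** The strongest reply is that the SAP handles the break openly. Exposure, compliance, days since last dose and disposition all account for it, and 6.5.2 discloses the mix. This stands. A reader might infer that the whole safety section treats these patients as continuously treated, and the documents do not support that. The gap is confined to the by-visit summaries and the onset table. Restricting Week 52 to description does not close it, because safety is summarised descriptively anyway (SAP 9). The optional modelling of safety parameters by the 8.5.1 method would leave Week 52 out, but the summaries and plots would not.

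Second, the condition on Table 4, read literally, already excludes a patient who is off drug. That is a fair reading of one sentence, but it leaves the value in neither table and sits badly with Section 6 and 6.5.2.1. The sections need reconciling on either reading.

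Third, 9.1 also summarises adverse events by treatment year. If the year boundary lies near Week 52, which the SAP does not say, restart events would fall in year 2. That helps, but it pools them with year 2 events in patients who never stopped.

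Fourth, placebo patients followed the same visit schedule and the same break. This is correct, so the comparison between arms is not confounded by the break. What remains is that the Week 52 contrast averages an on-drug and an off-drug contrast.

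Finally, development of the drug has stopped, significance levels are nominal (SAP 8.3), and by-patient listings will be available. This lowers the priority without supplying the missing rule.

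**Conclusion.** The point holds, as a cheap improvement. The SAP calls these patients off-treatment at Week 52 in one place and classes the same values as on-treatment in another, and its by-visit safety outputs have no split. The effect is limited to outcomes that reverse within four weeks; an effect already resolved by Week 48 would not be diluted. The 6% to 45% range rests on assumed off-drug shares and on eGFR changes from another disease, so it is not an estimate for this trial. Placing restart events in the later row assumes that onset is counted from first dose.

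Four stronger readings are tempting and are not supported:

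- **A share taken from calendar dates.** Take mid-May 2019 as the start, version 6 (4 February 2022) and the drug stop (10 May 2023). Subtracting 363 days from the last two gives 6 February 2021 and 12 May 2022. Uniform enrolment then gives 633/1093 = 58% off drug, or 813/1093 = 74% with a 180-day consent lag. Saying that only 26% to 42% of an effect would remain also assumes that nothing persists off drug. With the Alport ratio, 1 − 0.58 × 0.606 = 65% and 1 − 0.74 × 0.606 = 55% of the eGFR shift would remain. Uniform enrolment is itself doubtful, since the planned size rose from 300 to 550 to 850.
- **Lipids as a leading example.** The panel was added only in version 5, so patients randomised earlier had no scheduled Day 1 lipid value.
- **Dilution of the worst-value tables.** Extra values cannot lower a maximum or raise a minimum. The fault in 9.5.2 is misclassification between on- and off-treatment.
- **A proven restart risk.** The documents contain no data on events after a four-week break.

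**What to change.** - Reconcile SAP 6.5.2 with 6.5.2.1 and 9.5.2, so that values from the planned Week 48 to 52 break are not classed as on-treatment.
- In 9.5, 9.7 and 9.9, present Week 52 safety summaries and plots separately for patients on and off drug, using the split already in 7.1. Limit the off-drug column to the planned break, since permanent discontinuers go to Table 5.
- In 9.1.2, state the time origin for onset. Give separate rows to events that start during the break and to events in the 12 weeks after the Week 52 restart.

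The cost is SAP wording and one extra split on a category that the disposition table already needs. The drawback is smaller numbers in each Week 52 column.
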